A Blood management protocol was recently developed at the Cleveland Clinic whereby either confirmed or suspected anemic patients with abnormal uterine bleeding scheduled for surgical management are referred to Blood Management for assessment of laboratory studies (CBC, Ferritin, iron, TIBC, %Sat) and a care plan is development. Several factors are considered in designing a treatment plan including current blood loss, anemia symptoms, scheduled or upcoming procedures, and others. Treatment plans may include observation alone or oral iron versus intravenous iron. Iron deficiency is calculated using the Ganzoni calculation for patients receiving intravenous iron. Per the Blood Management Protocol: An anemia screening lab panel will be ordered, in combination with a referral to the Blood Management clinic via WHI Blood Management Referral Smartset. This order set will automatically preselect the lab panel — complete blood count (CBC), iron, total iron binding capacity (TIBC) and ferritin — and the referral to the Blood Management clinic. The patient will automatically receive information in the after-visit summary regarding the Blood Management clinic referral. Any correctable causes of anemia will be addressed preoperatively by the Blood Management group. Measures used may include the use of intravenous iron or oral iron. See Algorithm in Table 2.0.

Using Ganzoni Formula Calculator: http://www.al-nasir.com/www/PharmCalc/mob exec calc.php?ID=ganzoni

Clinical data for calculator:

- a) Current hemoglobin
- b) Weight in kg
- c) Target hemoglobin (see table below)

Ganzoni Target Hemoglobin	Female
High Blood Loss* (> 3 gm/dL)	13 gm/dL

Low Blood Loss* (1-2 gm/dL)	12 gm/dL
Non-surgical*	12 gm/dL
Unknown*	12 gm/dL

*High blood loss defined as expected drop in hemoglobin > gm/dL postoperatively i.e. CABG, Valve, AAA, lower extremity joint replacement,multi-level spine w/instrumentation; Low blood loss expected drop hemoglobin 1-2 gm/dL i.e. hysterectomy, simple colectomy, laparoscopic or robotic assisted procedures; Non-surgical is medical iron deficiency treatment; Unknown are default targets.

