Race • Gravidity/Parity Prior abdominal surgery Prior cesarean section Diabetes Hypertension **Current Smoker** Former Smoker • Menopause status Type of surgery: Hysterectomy or myomectomy Type: Vaginal, laparoscopic, open, laparoscopic assisted vaginal hysterectomy, robotic • Surgery date, discharge date • Surgery date/ Discharge date • Subject email Primary objectives: • Change in hemoglobin levels o Baseline Hemoglobin (pre-op) o Post Op Hemoglobin level Secondary objectives: • Operative time Blood Loss • Perioperative transfusion rate • Length of hospital stay • Intraoperative Complications o Intraoperative injuries o Post-operative infection rates Readmission Reoperation • Patient Satisfaction • Quality of Health and Recovery • Number of infusions received • Days on PO iron therapy

Table 1.0 -- Data Collection Variables

We anticipate that patients undergoing blood management protocol will have a faster return to normal recovery and better quality of life scores during recovery using the RAND-36 assessment questionnaire compared to patients undergoing usual care. We also plan to evaluate additional cost of blood management treatments for oral iron, IV iron, and blood transfusion in regards to feasibility, and from a health care utilization standpoint.

Methods and Study Design:

This will be a prospective randomized control trial conducted in a single large-referral center where anemic patients undergoing hysterectomy for fibroids or abnormal uterine bleeding will be recruited and randomized to undergo Blood Management protocol or usual care.

Inclusion criteria are anemic patients (defined as Hgb ≤ 11g/dL within 30 days of initial MIGS consult visit), greater than 18 years of age, with abnormal uterine bleeding, or fibroids undergoing hysterectomy by laparoscopic, robotic, vaginal or open routes. Exclusion criteria are malignancy, pregnancy, sickle cell anemia or other blood dyscrasias, women who received blood transfusions in 30 days prior to surgery, women receiving EPO therapy, women who have undergone gastric bypass surgery, and women on therapeutic/full anticoagulation. Patients undergoing hysteroscopic myomectomy alone without will not be included in the study.

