Women meeting the above inclusion criteria who are undergoing elective surgery (hysterectomy) at the Cleveland Clinic Main Campus will be randomly allocated to receive presurgical optimization blood management referral versus usual care - defined as expectant management with no therapy, or PO iron therapy at the primary surgeon's discretion. Randomization following a computer generated number sequence and allocation will occur in person. Patients will be screened from multiple minimally invasive gynecologic providers with high volume surgical practices at a large teaching institution, and consented on their initial preoperative visit. (These MIGS surgeons are [name], [name], [name], [name].) Patients will be randomized to receiving a blood management referral or usual care. Patients will be randomized with permuted block randomization with block size 2 and stratified on care providers. Blood management work up protocol is visible in Table 1. Patients receiving usual care will receive anemia management provided by the primary physician that may include no treatment, continued observation, or oral iron recommendations in the pre-operative time.

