The intervention will include pre-surgical optimization blood management referral based on preoperative Hb levels ≤11.0. Currently it is not standard of care at the Cleveland Clinic to send all patients with Hb ≤11.0 due to secondary anemia to blood management. It is done currently at the provider/surgeons preference alone and not through a research protocol or guidelines. At the initial consultation visit a CBC will be drawn, patients will be given a consent form for the study and asked to review it. If a Hb ≤11.0 within 30 days of consultation visit is documented in EPIC, they will be consented and randomized at the consultation visit. All patients after initial consultation visit will be immediately sent to the lab for blood draw if they have not had Hb drawn within 30 days. Lab draw includes: CBC + differential, iron studies: iron, TIBC, ferritin, optional B12. If the initial consult visit occurs at Fairview or Hillcrest Hospital, the patient's follow up preoperative visit will be scheduled at the main campus where consent will be obtained. The blood management team then will receive the referral from primary surgeon's office via EPIC inbasket. Blood management coordinator will assess patient, arrange treatment, and orders will be cosigned by surgeon/referring provider. Blood management may further assess for symptoms of PICA, restless legs, and cold intolerance as symptomatic indicators of anemia. The Rand 36 study will be administered at either the consultation or the pre-operative visit. The PATSAT 35 will be administered at the postoperative visit only. Postoperative Hb levels will be collected by a CBC at the post-operative visit. All postoperative visits will be scheduled at the main campus. All surveys and consents will be obtained at visits that occur at the main campus.

[figure not shown]

Table 2: Blood Management Preoperative Iron Deficiency Algorithm

Blood loss intraoperatively will be measured as accurately as possible with suction device recording and quantitative blood loss and tapes/packs by weighing instead of only visual assessment.

[figure not shown]

Image: 1.0 -- Patient Flow Sheet

Justification for Sample Size:

Power Calculation:

Sample size was calculated to have 80% power to detect a difference between groups using a T-test at a significance level of 0.05. We assume that patients at 4 weeks will have a standard deviation in hemoglobin values of 1.2 g/dL (8) to detect a 1 g/dL difference between groups, we

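### The transfusion exclusion counts back from surgery, which follows randomization, so it cannot be fully checked at entry and, applied as written, could make a randomized woman ineligible.

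*Combined protocol and SAP*

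**What the plan says.** The exclusion list in Methods and Study Design includes "women who received blood transfusions in 30 days prior to surgery". The anemia criterion in the same section is anchored differently: hemoglobin of 11 g/dL or less "within 30 days of initial MIGS consult visit".

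On timing, women with a documented qualifying hemoglobin "they will be consented and randomized at the consultation visit". Women without a recent value "will be immediately sent to the lab for blood draw if they have not had Hb drawn within 30 days"; the plan does not say when they are then randomized. For women first seen at the two other hospitals, the "follow up preoperative visit will be scheduled at the main campus where consent will be obtained". Another sentence places consent at the first preoperative visit. In every case women "will be randomly allocated to receive presurgical optimization blood management referral versus usual care", so allocation precedes surgery.

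On the arms, usual care "may include no treatment, continued observation, or oral iron recommendations in the pre-operative time". For Blood Management, the Background states: "Treatment plans may include observation alone or oral iron versus intravenous iron".

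The primary outcome in Specific Aims/Objective is the change from a hemoglobin taken in the 72 hours before surgery to one taken 4 weeks after it. The Analysis plan lists the tests. It names no analysis population and gives no rule for women who meet an exclusion after randomization.

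**The concern.** An eligibility criterion should be decidable by the time of randomization. This one is not, because its window closes at surgery. A woman can be eligible when allocated and meet the exclusion two weeks later.

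If such women are then left out, they are selected on an event that occurs while the assigned preoperative care is being given. Both arms may receive observation or oral iron, but intravenous iron appears in the description of Blood Management and not in that of usual care. Transfusion before surgery could therefore depend on the arm. That is an inference: the documents give no preoperative transfusion rate, and the evidence in the Background mainly concerns transfusion around or after surgery. If it is right, removal breaks the randomized comparison for the primary change score and for every secondary outcome. If no rule is set in advance, each case will be decided after allocation.

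**Working it through.** **Inputs.** Justification for Sample Size: SD 1.2 g/dL, difference 1 g/dL, t-test at 0.05 (sidedness not stated, taken as two-sided), 80% power, 24 evaluable and 30 enrolled per group, 20% dropout. Assumed, because the documents give no figures: days T from randomization to surgery, the number k of women affected, and the size of their deviation in hemoglobin.

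**1. The plan's own figure.** A two-sample t-test (noncentral t) with effect size 1/1.2 needs 23.6, rounded up to 24 per group. Power at 24 per group is 80.7%. Enrollment is 48/0.8 = 60. The stated figures reproduce and are not in dispute.

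**2. Share of the window that follows randomization**, min(T, 30)/30:

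| T (days, assumed) | Share after randomization |
|---|---|
| 7 | 7/30 = 23% |
| 14 | 14/30 = 47% |
| 21 | 21/30 = 70% |
| 30 or more | 100% |

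**3. Shift if k of 30 women are removed from one arm only.** If their mean change differs from the full-arm mean by D, the remaining mean moves by −k·D/(30 − k). In absolute size:

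| k | \|D\| = 1 g/dL | \|D\| = 2 g/dL |
|---|---|---|
| 1 | 1/29 = 0.03 | 2/29 = 0.07 |
| 2 | 2/28 = 0.07 | 4/28 = 0.14 |
| 3 | 3/27 = 0.11 | 6/27 = 0.22 |

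The sign depends on D, which is unknown.

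**4. Removal from both arms.** With 3 women against 1, all with the same D, the net shift is 3/27 − 1/29 = 0.08 g/dL at |D| = 1 and 0.15 at |D| = 2. Equal removal of similar women cancels.

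**5. Power.** After 20% dropout the affected arm has (30 − k) × 0.8 = 23.2, 22.4 or 21.6 women, against 24 in the other. Power is 80.0%, 79.2% or 78.4%, compared with 80.7%.

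**6. Effect of keeping the women instead.** If k of 30 have the 72-hour value raised by r, the arm's preoperative mean rises by k·r/30. For k = 1, 2, 3 this is 0.03, 0.07, 0.10 g/dL at r = 1 and 0.07, 0.13, 0.20 at r = 2. It is an upper bound on the effect on the change score if the 4-week value is raised as well.

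**The case against.** The strongest reply is that nothing in the text withdraws a randomized woman for a later transfusion. The item stands in a list of entry criteria beside pregnancy and malignancy, which can also arise after randomization, and nobody would take those as removal rules. Allocation is of women who meet the criteria, which fits use at screening only. On that view, what remains is the general absence of an analysis-population statement. Much of this stands: a reader might infer that the protocol orders removal, and it does not. But this criterion differs from its neighbours because its own wording sets a window that ends at surgery. Used at screening only, it covers part of the 30 days, or none if surgery is 30 or more days away.

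A second reply is that a transfusion-free month before surgery protects the 72-hour hemoglobin. This is a sensible motive, but the documents do not state it, and a supportive analysis can serve it.

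Third, the patient flow sheet is not shown in the text available and might mark the eligibility check; that absence is no fault of the plan. No check made by the time of randomization can detect a later transfusion, though the sheet might say what is then done. The planned costing of blood transfusion also suggests that some transfusions will be captured, but it does not settle who is analysed.

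**Conclusion.** The point holds as a minor one. The criterion cannot be fully checked at entry, and the plan does not say whether a woman transfused between randomization and surgery stays in the analysis. One-sided removal of 1 to 3 of 30 women would move an arm's mean by 0.03 to 0.22 g/dL against the 1 g/dL target and cost at most 2.3 points of power (80.7% − 78.4%). These figures rest on assumed numbers removed and assumed deviations of 1 to 2 g/dL. The true size is unknown and probably small.

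Three stronger readings are not supported:

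- **That the result would be biased in favour of one arm.** The sign of D is unknown, and dependence on the arm is itself inferred.
- **That the transfusion rate would be understated.** This requires the peri-operative window to include the days before surgery, which the protocol does not define. The one rate it cites is for hysterectomy overall and not for women with hemoglobin of 11 g/dL or less, so no figure is offered.
- **That admitting a woman transfused shortly before consultation, with surgery more than 30 days later, is a further bias.** She is eligible whether the criterion is applied at screening only or up to surgery. This follows from the look-back chosen.

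**What to change.** 1. Anchor the exclusion to randomization: *received a blood transfusion in the 30 days before randomization, or between the qualifying hemoglobin and randomization*. The second clause matters when consent comes at a later preoperative visit and the qualifying sample is more than 30 days old.
2. State that a transfusion between randomization and surgery does not remove a woman from the trial or the analysis, and that all randomized women are analysed in their assigned groups.
3. Record transfusions between randomization and surgery by arm, and report them separately from intra- and postoperative ones.
4. State that the primary change score uses the observed 72-hour hemoglobin whether or not the woman was transfused after randomization. Add an analysis excluding transfused women, labelled supportive.

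None of this touches transfusion practice. The cost is a few sentences and one data field. A few women become ineligible: one transfused 25 days before consultation, randomized there and operated on 40 days later, is eligible now (25 + 40 = 65 days before surgery) and would be excluded, so recruitment may slow slightly. Some 72-hour values will partly reflect transfusion, by about 0.03 to 0.20 g/dL on the arm's preoperative mean under the assumptions above. That is about as large as the removal shift. The gain is that the groups compared are those randomized, not that the shift is smaller.

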There is currently limited information regarding the role of blood management in the benign gynecologic population and specifically, in patients who are scheduled to undergo surgery for fibroids and/or abnormal uterine bleeding. A thorough search through PubMed and clinicaltrials.gov did not reveal any studies on this issue. In 2019 at CCF only 2% of gyn patients at Main Campus were referred to blood management, but 12.6% of the main campus gyn population had a Hb of <10.0 g/dL. The overall goal of this study is to evaluate the role of preoperative blood management in optimizing surgical outcomes by reducing the co-morbidities associated with postoperative blood transfusion.

Specific Aims/Objective:

The primary objective of this study is to compare the change in baseline hemoglobin levels in patients in the study (Blood Management Protocol) and control ("usual care")

group who are undergoing hysterectomy for abnormal uterine bleeding. Change in baseline hemoglobin levels is defined as the difference of the hemoglobin level obtained within 72 hours prior to surgery and the hemoglobin level at 4 weeks postoperatively.

Our secondary objectives include 1. To evaluate the perioperative outcomes between the two groups including OR times, EBL, peri-operative transfusion rates, length of hospital stay, complications including intra-operative injuries, postoperative infection rates, readmission, and re-operation; 2. to assess patient satisfaction regarding their experience with the Blood Management protocol and extra outpatient infusion visits required using a patient questionnaire (PATSAT 35, Attached); and 3. to compare the quality of patient health and recovery between the two groups using the RAND-36 (Attached) assessment tool. The REDCap database will include potential identifiers to enable online surveys. The included potential patient identifiers include: date of birth, surgery date, and subject email (they provide for the study.)

Data variables that will be collected in the study are visible in the following table.

Patier	nt Demographics:
•	MRN
•	Age/ Date of Birth
•	BMI

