will need 48 patients total (24 per group) if the groups are of equal size. Assuming a 20% dropout rate, 60 patients total (30 per group) will be the target enrollment.

Cost and Payments to Subjects

The patients will have no additional costs due to participating in the study beyond the usual insurance copays and standard costs for appointments.

Quality Control Procedure:

Information will be provided to all department members involved in administration of the study. Follow up, data entry, and patient follow up will be closely followed by the research team (resident, fellow, staff physicians, MIGS NP's, Lead research nurse)

Process of Consent

Patients would be consented for participation in the study at their primary surgeon's office when shared decision making for proceeding with surgery is performed. Patients will receive no difference in care based on their participation in the study apart from the study protocol

Risks and Discomfort of the Project

The study has been designed to minimize as much risk as possible, and participants will be subjected to no more than minimal or standard risk for undergoing the intervention. Breach of confidentiality is a small risk. Physical risk are rare and unanticipated but would be limited to transfusion reaction to the IV iron therapy. There are no psychological risks for patients who participate in this study. Participants can also benefit from their participation in this study due to their altruistic motivation for partaking in research study they have contributed to scientific advancement.

Analysis plan

Approximately normally-distributed continuous measures will be summarized using means and standard deviations and will be compared using two-sample t-tests. Continuous measures that show departure from normality and ordinal measures will be summarized using medians and quartiles and will be compared using Wilcoxon rank sum tests. Categorical factors will be summarized using frequencies and percentages and will be compared using Pearson's chi-square tests or Fisher's Exact tests. All analyses will be done using SAS (version 9.4, The SAS Institute, Cary, NC) and a p < 0.05 will be considered statistically significant.

Timetable:

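### Fixed blocks of 2 within surgeon, with no blinding described, make 28 to 30 of 60 allocations certain in advance to anyone tracking them: an avoidable selection-bias risk

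*Combined protocol and SAP*

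**What the plan says.** The randomization rule is in Methods and Study Design: "Patients will be randomized with permuted block randomization with block size 2 and stratified on care providers". The same paragraph lists four surgeons. It says the sequence is computer generated and that assignment is made face to face. One block size is given, and no way of releasing an assignment under concealment is described. No blinding of surgeon, patient or assessor is described in the text. The patient flow sheet is a figure that is not shown.

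The surgeon's side of the trial sees the allocations:

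- Process of Consent: "Patients would be consented for participation in the study at their primary surgeon's office".
- Methods and Study Design, on the intervention: "The blood management team then will receive the referral from primary surgeon's office via EPIC inbasket", and "orders will be cosigned by surgeon/referring provider".
- In the control arm, whether oral iron is given is left to the primary surgeon.

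On present practice in referring anemic patients, Methods and Study Design says: "It is done currently at the provider/surgeons preference alone and not through a research protocol or guidelines".

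**The concern.** A 1:1 block of size 2 holds one assignment to each arm. Once the first is known, so is the second. Stratifying by surgeon turns the sequence into short lists of each surgeon's own patients, which are easy to follow. The block size is printed in the protocol. Concealing the list does not help, because the visible arm of the first patient reveals the second.

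The condition is that someone involved in approaching patients keeps track. The documents do not say who does the approaching. Entry rests on a laboratory cut-off (Hgb ≤ 11 g/dL), and consent comes before randomization. The room to steer is therefore mainly whether and when an eligible woman is approached. A motive is plausible, because referral is now a matter of each surgeon's preference.

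The analysis would not reliably repair a resulting imbalance. Under the Analysis plan, roughly normal continuous measures "will be compared using two-sample t-tests", with no adjustment for baseline or surgeon. The primary outcome is a change score, but Specific Aims/Objective puts its starting point after the intervention: "Change in baseline hemoglobin levels is defined as the difference of the hemoglobin level obtained within 72 hours prior to surgery". It therefore offsets a difference in enrolment hemoglobin only in part. Transfusion and the other secondary outcomes lack even that offset.

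**Working it through.** **Inputs.** Block size 2, stratified by care provider, four surgeons listed (Methods and Study Design). Enrolment of 60 in two equal arms; SD 1.2 g/dL, difference 1 g/dL, 80% power, alpha 0.05, 20% dropout (Justification for Sample Size).

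**Assumptions.** The four listed surgeons are the strata. The observer sees all earlier allocations in a stratum and knows the possible block sizes. The t-test is two-sided.

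**1. The plan's own figure.** A two-sample t-test with these inputs needs 23.6, so 24 per arm (power 80.7%). That is 48 in total, and 48 / (1 − 0.20) = 60. The sample size reproduces and is not affected by this point. The plan gives no figure for predictability.

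**2. Allocations certain in advance, blocks of 2.** In a stratum of n_i patients, floor(n_i/2) are second in their pair. Over all strata the sum is (60 − k)/2, where k is the number of strata with an odd count. Four counts that add to 60 allow only k = 0, 2 or 4.

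| Odd strata | Certain | Share of 60 | Best-guess rate |
|---|---|---|---|
| 0 | 60/2 = 30 | 50% | (30 + 0.5 × 30)/60 = 75.0% |
| 2 | 58/2 = 29 | 48% | (29 + 0.5 × 31)/60 = 74.2% |
| 4 (e.g. 15 each) | 56/2 = 28 | 47% | (28 + 0.5 × 32)/60 = 73.3% |

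The best guess takes the certain assignments as known and the rest at even odds. Simple randomization gives 50%.

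**3. If the number of strata is not four.** The minimum is (60 − largest even number not above the number of strata)/2. This gives 29 for two or three strata, 27 for six and 26 for eight. The maximum stays 30.

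**4. Other block schemes.** Simulation with 1,500 trials for each of five splits of 60 (15/15/15/15, 16/16/14/14, 24/18/12/6, 21/17/13/9, 30/15/10/5), using exact Bayesian prediction:

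| Scheme | Certain, of 60 | Best-guess rate |
|---|---|---|
| Fixed 2 (exact) | 28–30 (47–50%) | 73–75% |
| Fixed 4, size known | 17.4–18.7 (29–31%) | 69–70% |
| Random mix of 4 and 6, possible sizes known | 3.5–3.7 (about 6%) | 67.6–68.3% |

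**5. What the change costs in balance.** The largest arm difference within a stratum is half the largest block: 1 with size 2, and 3 with the 4/6 mix. Over four strata the theoretical worst cases are 4 × 1 = 4 and 4 × 3 = 12. In simulation the overall difference with the 4/6 mix has median 2 and 95th percentile 4, and exceeds 6 in at most 0.1% of trials. With 48 analysed, power is 80.7% at 24/24, 80.4% at 26/22 and 80.1% at 27/21.

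**The case against.** Several points on the other side deserve weight.

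- **No single surgeon knows 28 to 30.** Blocks run within surgeon, so each can foresee only the second of each pair in their own stratum: 7 of 15 with an equal split, and between 2 and 15 over the splits above. This is right. The 28 to 30 is a trial-wide total, reached only if allocations are tracked in every stratum.
- **Four strata is an inference.** The plan stratifies on care providers and lists four surgeons without saying that these are the same. This too is right, but the count stays between 26 and 30 for two to eight strata.
- **The procedure leaves little room to steer.** Methods and Study Design has the consent form given out at the first visit. Women with a documented qualifying hemoglobin are then consented and randomized at that visit, so steering them would mean departing from the plan. There is more room with women awaiting a laboratory result or first seen at another hospital. This lowers the likelihood of bias but does not remove the predictability.
- **Motive may be weak.** The background reports that in 2019 only 2% of main-campus gynecology patients were referred, while 12.6% had hemoglobin below 10.0 g/dL. Referral was uncommon, which does not show a strong preference for it. Nor does it exclude selective referral.
- **The remedy is partial.** The best-guess rate falls only from 73–75% to about 68%. That is so; the gain lies in removing certainty.

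None of these points to text that prevents the second assignment of a pair from being known.

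**Conclusion.** The concern holds and should be fixed. Following the rule as written, the second assignment of each pair is certain to anyone who knows the block size and the previous allocation in that stratum. Trial-wide this is 28 to 30 of 60 allocations, with a best-guess rate of 73–75%. The arithmetic is exact for four strata and changes little for other numbers.

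What follows is a risk and not a demonstrated bias. It depends on someone who approaches patients tracking the allocations and acting on them. The documents do not settle how likely that is, and the flow sheet is not available. That the change score gives only partial protection is an argument from the timing of its baseline, not a calculation. The size of any bias in hemoglobin change cannot be derived from the documents.

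**What to change.** In Methods and Study Design, replace the fixed block size with randomly varying block sizes within surgeon, for example 4 and 6. Keep the sizes out of the protocol and known only to the statistician. Add that each assignment is released only after consent and eligibility have been recorded, for example through REDCap, which the study already uses. This keeps the plan's order of consent and then randomization and adds a concealed release step. It is best done before enrolment starts, because allocations already made cannot be concealed afterwards.

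The statistician regenerates the list and one or two sentences change. The downside is slightly looser balance: a typical overall arm difference of 2, rarely above 4. Even a difference of 6 among the 48 analysed costs 80.7 − 80.1 = 0.6 percentage points of power.

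### The written schedule has no postoperative RAND-36, although secondary objective 3 is about recovery, and the preoperative RAND-36 is not tied to randomization

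*Combined protocol and SAP*

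**What the plan says.** Specific Aims/Objective sets the third secondary objective: "to compare the quality of patient health and recovery between the two groups using the RAND-36". The same section, after Table 1.0, anticipates for the intervention arm a "faster return to normal recovery and better quality of life scores during recovery using the RAND-36 assessment questionnaire". No other instrument is named for this objective.

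Methods and Study Design gives the only RAND-36 timing: "The Rand 36 study will be administered at either the consultation or the pre-operative visit". The next two sentences deal with the postoperative visit: "The PATSAT 35 will be administered at the postoperative visit only" and "Postoperative Hb levels will be collected by a CBC at the post-operative visit". The primary objective places that hemoglobin value in time as "the hemoglobin level at 4 weeks postoperatively".

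On allocation, the same section says of patients who already have a qualifying hemoglobin on record that "they will be consented and randomized at the consultation visit". For patients first seen at Fairview or Hillcrest, a "follow up preoperative visit will be scheduled at the main campus where consent will be obtained". Surveys and consents are confined to main-campus visits. The Analysis plan gives generic two-sample tests and names no RAND-36 time point, change score or baseline adjustment.

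**The concern.** There are two gaps.

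First, recovery can only be measured after surgery, and the prose schedules the RAND-36 only before it. Staff working from the text would have no instruction to give it again. A 4-week score that was not collected cannot be recovered later, so objective 3 would have no data.

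Second, the preoperative score has no fixed position relative to randomization. A patient randomized at the consultation may, under the text, complete the RAND-36 at a later pre-operative visit, after learning her allocation and possibly after receiving iron. The order of survey and randomization within the consultation is not stated either. The first scores may therefore mix values from before and after allocation. A score taken after allocation may already reflect the allocation or the treatment, so it cannot safely serve as a covariate or as the starting point of a change score.

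**Working it through.** **Schedule against objective.** The first gap needs no arithmetic, only the statements side by side.

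| Item | What the text provides |
|---|---|
| Objective 3 and its hypothesis | RAND-36 compared between arms, during recovery |
| RAND-36 timing | Consultation or pre-operative visit |
| Procedures named for the postoperative visit | PATSAT 35; CBC |
| Location rule for surveys | Main campus (fixes place, not time) |
| Analysis plan | No RAND-36 time point |

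Neither of the two procedures named for the postoperative visit is the RAND-36.

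**Timing against randomization.**

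- Qualifying hemoglobin on record at the consultation: randomized there. A RAND-36 at that visit may come before or after allocation. One at the later pre-operative visit comes after it.
- First seen at Fairview or Hillcrest: consent is taken at the later main-campus visit. A survey there can precede allocation, but the text does not require it.
- No hemoglobin within 30 days: sent to the laboratory after the consultation, so eligibility may be known only later. The order of survey and allocation is again not stated.

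The documents do not allow the share of first scores taken after allocation to be calculated.

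**What a clean baseline is worth.** Inputs from Justification for Sample Size: 80% power, alpha 0.05 (two-sided assumed), SD 1.2 g/dL, difference 1 g/dL, 24 per group, 20% dropout.

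1. The plan's own figure. The standardized difference is 1/1.2 = 0.833. The two-sample t-test needs 23.6 per arm, rounded up to 24, so 48 in total, and 48/0.80 = 60 enrolled. Power at 24 per arm is 80.7%. The stated sample size is reproduced.
2. Unadjusted comparison of postoperative RAND-36 scores. Solving the noncentral t for n = 24 per arm gives a detectable difference d = 0.826 SD.
3. Adjusted for a pre-randomization score with pre-post correlation r. The detectable difference is d × √(1 − r²), neglecting the degree of freedom spent on the covariate, and the residual variance falls by r². The documents give no value of r, so a range is assumed.

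| Assumed r | Detectable difference | Reduction in variance |
|---|---|---|
| 0.3 | 0.826 × √0.91 = 0.788 SD | 9% |
| 0.5 | 0.826 × √0.75 = 0.715 SD | 25% |
| 0.7 | 0.826 × √0.51 = 0.590 SD | 49% |

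**The case against.** The strongest reply is that the flow sheet (Image 1.0) is not visible in the reviewed copy and is a natural place for a visit-by-visit survey schedule. The sentence confining the PATSAT 35 to the postoperative visit can also be read as a contrast with a RAND-36 given at more than one visit. The hypothesis and the entry for quality of health and recovery in Table 1.0 show that measurement in recovery is intended. On this reading a clause was left out, and the objective itself is sound. That is plausible, and it limits the finding to the readable text. It does not remove the gap: the PATSAT sentence assigns the RAND-36 to no visit, and if the flow sheet does show a postoperative survey, the text disagrees with it and still needs correcting.

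On the second gap, campus logistics may explain the wording. If surveys simply accompany consent at the main campus, the choice of visit follows from where the patient was first seen. But the protocol does not state that rule, and nothing places the survey before allocation.

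It is also fair to say that no baseline-adjusted RAND-36 analysis is planned, and that an unadjusted comparison of postoperative scores at a fixed visit is valid whatever the preoperative timing. That stands. The figures above measure the precision a clean baseline would buy. They do not measure a bias, and they do not measure the harm from a missing postoperative survey.

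**Conclusion.** Both gaps hold on the readable text. As written, the schedule yields no RAND-36 score during recovery for up to 60 enrolled patients (48 expected completers), so objective 3 could not be answered by following it. This is conditional on the flow sheet: if that shows a postoperative administration, the fault reduces to an incomplete text.

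The loose preoperative timing is the lesser matter. It does not invalidate an unadjusted postoperative comparison, but it puts at risk a gain from a detectable 0.83 SD to 0.79, 0.72 or 0.59 SD. That gain rests on assumed correlations of 0.3, 0.5 and 0.7, on 24 completers per arm and on a two-sided 0.05 test. Only a secondary objective is affected. The point should be corrected, and confidence is moderate because the flow sheet could not be seen.

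**What to change.** State in Methods and Study Design, and make the flow sheet agree, that every patient completes the RAND-36 twice:

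1. at the main-campus consent visit, before the allocation is revealed;
2. at the existing 4-week postoperative visit, with the PATSAT 35 and the CBC.

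In the Analysis plan, name the 4-week RAND-36 score as the quantity compared between arms, preferably adjusted for the pre-randomization score and for care provider, the stratification factor, to gain precision.

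Reword the hypothesis to match. A single postoperative score supports a comparison of level at 4 weeks. It cannot show how quickly patients return to normal.

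The cost is one or two sentences in the schedule, short matching edits to the Analysis plan and hypothesis, and one more questionnaire at a visit that already takes place, with online surveys in REDCap already planned. The primary endpoint and sample size do not change.
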